10.2.2 Patient and Clinic Stakeholder Focus Groups

We will begin each focus group with a review of the prioritized barriers to engagement (primary objective) and targets for potential adjunct interventions (interviews from secondary objective). To ensure that this discussion is as salient as possible to stakeholders, we will present each barrier using quotes from patients who experienced the barrier. We will briefly elicit participants' perceptions of how these barriers impede engagement as we anticipate that the group discussion will provide additional insight. We will then present participants with potential adjunct interventions to target these barriers (Table 7), identified through the existing literature. We will elicit feedback from stakeholders regarding the anticipated effectiveness and feasibility of these interventions in their clinical settings, and needed adaptations. We anticipate that adaptation will be necessary, as identified interventions are not likely to have been developed within clinics caring for a high proportion of disadvantaged patients. We will then prompt participants to brainstorm other solutions to address prioritized barriers. At the completion of the focus group, we will use nominal group technique to identify three interventions perceived to have the greatest potential.^{92,93} We will ask stakeholders to evaluate each

Table 7. Examples of possible interventions

Intervention	Goal for Patient	Target Barrier
Delivery using electronic health record	Decrease barriers to access	Accessibility
Pre-consult pairing with decisional coach	Improve preparation	Preparatory
Intervention to increase family member participation	Increase confidence in interacting	Interactional
Intervention to increase surgeon facilitative behaviors	Increase perception that input is valued	Interactional

intervention using a modified Ottawa Acceptability tool.⁹⁴

11.0 END OF INTERVENTION/STUDY

11.1 Duration of Study

Site level participation will end when the last patient enrolled completes their breast cancer treatment. A subset of sites will have a focus group conducted using their patients. For those sites, participation will end when that focus group is completed.

Clinic stakeholder participation ends when the last patient enrolled completes her surgical consultation. For the subset of clinic stakeholders that will participate in the focus groups, study participation concludes at the end of that focus group.

Patient-level participation surveys and audio-recording will end after they complete the follow-up survey. Chart reviews for them will be completed after their breast cancer treatment is complete to accurately reflect care received. For the subset of patients who participate in the interview and/or focus group, study participation concludes at the end of that interview/focus group.

Please see the study calendar (Section 5.0) for follow up time periods.

11.2 Criteria for Discontinuation of Study

In the absence of study procedures due to adverse event(s), patient participation may continue until one of the following criteria applies:

- Patient explicitly decides to withdraw from the study
- Termination of the study by sponsor

If a patient has a subsequent decline (such as opt-out from an interview), the decline applies only to that specific research activity and does not apply to any prior data collection unless specified by the patient.

11.3 Follow-up

11.3.1 Duration of Follow-up

Following the surgical consult where informed consent was obtained, the baseline survey (T0) completed, and consult audio-recorded (T1), a follow-up survey (T2) will be emailed to patients within 24 hours of the consultation. If no response is received, study staff will send reminders to the patient via email and telephone calls (maximum of six attempts), with the goal of completing the survey within 3 weeks. To avoid missing data, study staff will also approach patients for survey completion at a follow-up visit if this is scheduled within the 3-week period. Patients will have chart review performed after completion of their breast cancer treatment.

11.3.2 Lost to follow up

Patients will be considered lost to follow up if attempts to reach them for the follow-up survey (T2) is unsuccessful. However, patients will still have their chart review performed, unless the patient explicitly decides to withdraw from the study and withdraws consent.

11.4 Managing Ineligible Patients

Baseline data and all post-baseline data up until the point the patient was found to be ineligible must be submitted; however, no data is required following the point that the patient was found to be ineligible. The patient should complete the consent withdrawal form and indicate “consent withdrawal for all follow up.”

12.0 STATISTICAL CONSIDERATIONS

As part of Update #06, the statistical considerations and analysis plan for the co-primary objectives have been amended. The rationale for these revisions was twofold. First, we needed to revise the primary analysis plan to address the current challenges, which were related to the COVID pandemic. Second, we needed to ensure that the revised primary analysis plan was compatible with the power calculations and that the power calculations reflected what realistic effect sizes the study would now be able to detect given these challenges. The amended statistical considerations and analysis plan for the co-primary objectives are detailed below.

12.1 Analysis Plan for Co-Primary Objectives

12.1.1 Primary Analysis

Co-Primary Objective #1: The goal is to evaluate the effectiveness of a decision aid in increasing patient engagement in decision making in clinics serving a high proportion of socioeconomically disadvantaged patients. We will follow an intention to treat approach, using all available data, regardless of group assignment or whether patients viewed the decision aid. The data as collected will have a nested structure: patients nested within surgeons within surgical clinics, this last level being the formal level of intervention. Descriptive analyses will summarize patient, surgeon, and clinic characteristics. When reporting these summary data, we will report as “NR-Not reported” any cell where the number of patients is less than five to avoid inadvertent patient identification. We will test intervention effects in the framework of generalized linear mixed effects models with an “intervention versus usual care” dummy variable (which varies over patients within each surgeon and clinic), a surgeon random effect, and a clinic random effect. Analysis models will include two additional parameters, for wave and wave-squared, respectively to flexibly control for potential time effects and to allow for a non-linear relationship with outcome measures. We will include a post-COVID restart dichotomous variable that reflects whether a patient is enrolled during the post-COVID restart time period for a given site (yes/no). We also will include time (in units of wave) post-COVID in all models. These indicator and time parameters allow for the control of sites restarting the trial post-COVID shut down at different times. This leads to the following planned linear mixed effects model for the two primary outcomes (y) in Aim 1, namely, PEPPi-5 self-efficacy and Active Patient Participation Behaviors:

$$y_{ijk} = \beta_0 + \theta x_{ijk} + \beta_1 t_{1ijk} + \beta_2 t_{1ijk}^2 + \beta_3 z_{ijk} + \beta_4 t_{2ijk} + u_k + u_{j(k)} + e_{i(j(k))}$$

Here, y_{ijk} denotes the response of the i^{th} level-1 unit (patient) of the j^{th} level-2 unit (surgeon) of the k^{th} level-3 unit (clinic). The variable x_{ijk} ($=0, 1$) denotes the intervention status of patient i from surgeon j within clinic k . The variables t_1 ($=1, 2, 3, 4, 5, 6, 7$) and t_1^2 ($=1, 4, 9, 16, 25, 36, 49$) are the linear and quadratic terms for wave with the corresponding coefficients β_1 and β_2 representing the fixed linear and quadratic effects to model the underlying secular trend. The variable z ($=0, 1$) denotes if patient i was enrolled during the post-COVID restart time period for a given clinic with the corresponding fixed effect coefficient β_3 . The variable t_2 ($=0, 1, 2, 3, 4, 5, 6$) denotes if patient i was enrolled within the first wave post-COVID restart time period ($t_2 = 1$); within the second wave post-COVID restart time period ($t_2 = 2$); and so on through the sixth wave post-COVID restart time period ($t_2 = 6$). The maximum value is $t_2 = 6$ because when the stepped-wedge design was suspended all clinics were at least enrolling part way in wave 2 of the possible 7 waves. For patients enrolled prior to the post-COVID restart time period the value of $t_2 = 0$. The random effect u_k is the level-3 (clinic) random intercept effect (random clinic variance); the random effect $u_{j(k)}$ is the level-2 random intercept effect for

the $j(k)^{th}$ level-2 unit (random surgeon variance nested in clinics); the random effect $e_{i(j(k))}$ is the random individual variance within surgeons nested in clinics. The term β_0 is the intercept. The term θ represents the intervention effect of the decision aid and is the primary effect of interest.

Models will adjust for the a priori specified patient characteristics described above that are likely to be strongly predictive of the endpoints. In the event that the approximately continuous outcomes PEPPi-5 self-efficacy and Active Patient Participation Behaviors are not approximately symmetrically distributed, variable transformation will be considered (e.g., square-root transformation). Further, as part of the planned efficacy analysis we will fully test the variance-covariance structure of the model, while blinded to any treatment effects, which may lead to a more parsimonious model.

We will use linear mixed effects models for the approximately continuous and symmetrically distributed outcomes (Active Patient Participation Behaviors, PEPPi-5, breast cancer knowledge, perceived knowledge) and logistic random effects models for binary outcomes (Decision Quality Instrument- Breast Surgery). Should count variable endpoints (e.g., Active Patient Participation Behaviors) exhibit floor effects, which we do not anticipate,⁹⁵ log-linear random effect models will be used to estimate the relationship of these endpoints to intervention group. In addition to accounting for association in the data at various levels of clustering, the mixed models will allow for estimation of the percentage of variance in outcomes accounted for by differences at the surgeon, and clinic level. This is critical as it will suggest at what level adjunct interventions may be most effective. Models will be estimated and tested using SAS v9.3 (PROC MIXED and PROC NLMIX).⁹⁶

Co-Primary Objective #2: The goal is to test the extent to which the effect of a decision aid on patient engagement is mediated through the mitigation of preparatory and interactional barriers, and determine if persistent barriers are disproportionately experienced by socioeconomically disadvantaged patients. As a decision aid can only be effective if patients are able to access/review it, we first assess for accessibility barriers to decision aid use. We will then examine the impact of preparatory and interactional barriers on engagement.

Accessibility Barriers: We will examine barriers to accessing the web-based decision aid separately, as only patients who receive the intervention can experience these barriers. Understanding accessibility barriers is critical to ensure the intervention will not worsen disparities. This is a largely descriptive analysis that will guide sampling and interview content for the patient interviews in Aim 3. We will calculate reach of the decision aid intervention for the study cohort, and for socioeconomically disadvantaged patients. We will summarize reasons why patients declined the decision aid. We will summarize other survey responses regarding decision aid accessibility (Table 5) and perform exploratory analyses evaluating the association with socioeconomic disadvantage, using chi-square tests and odds ratios for categorical variables and ANOVA mean differences for continuous variables, respectively. Due to the exploratory nature of the analysis, sample size and power are not calculated.

Preparatory and Interactional Barriers to Patient Engagement:

Decision Aid Impact on Engagement through Mitigation of Barriers

We will first perform analyses to test and quantify the extent to which the effect of the decision aid intervention on patient engagement endpoints is mediated through the mitigation of candidate preparatory and interactional barriers. We will quantify the indirect effect relative to the total effect of the decision aid in joint linear structural equation models (SEM) for the endpoint and the candidate mediators, including random surgeon effects and random region effects for each of the mediator and endpoint parts of the models. Each of the preparatory and interactional Barriers will be represented by a continuous latent construct in the SEM, with 3 and 5 observed items for Preparatory and Interactional Barriers, respectively. Binary or count variables will be modeled via latent continuous construct in the SEM. Structural equation models will be specified, estimated and tested using Mplus v7.3.⁹⁷ The use of unidimensional latent constructs increases power and reduces the number of tests, relative to testing each observed item separately. Standardized coefficient estimates from the SEM, representing total, direct, and indirect effects, will allow for the determination of whether the mechanism by which the decision aid leads to increased patient engagement is through the mitigation of preparatory and/or interactional barriers (see Figure 7 for simplified example). For example, if coefficient X is important but Y is not, we can conclude that although the decision aid leads to statistically significant changes in interactional barriers, this is not the mechanism through which the decision aid increases patient engagement. Alternatively, if only coefficient Y is important, we can conclude that although the interactional factors represent a significant barrier to patient engagement, the decision aid does not significantly impact the barrier.

Finally, if we find significant indirect effects (represented in the figure by the dashed line leading from the decision aid to engagement that runs through interactional barriers), we can conclude that receipt of the decision aid leads to a change in the interactional barrier, which leads to improved patient engagement. Statistically, coefficients X and Y will be tested together, with the null hypothesis being that the product $XY=0$. If either latent construct for preparatory or interactional Barriers is significant, then each individual observed item will be tested, post hoc, as candidate barriers. Candidate barriers for the next models will be barriers for which the indirect effect is significant and/or barriers associated with lower levels of engagement (i.e. coefficient Y). Those barriers associated with lower level of engagement will be considered persistent and prioritized for inclusion in the qualitative interviews (Aim 3).

Persistent Barriers Experienced by Socioeconomically Disadvantaged Patients

We will estimate logistic and Poisson regression models with socioeconomic deprivation as the explanatory variable, and each candidate persistent barrier as described above as the outcomes, in order to assess the extent to which socioeconomic disadvantage is associated with persistent barriers to engagement. As with Aim 1, models will include surgeon and clinic random effects to account for patient clustering. Findings will guide the sampling strategy for patient interviews (Aim 3) and will be incorporated into the interview content.

[figure not shown]

Figure 7. Schematic depicting the mediating role of preparatory and interactional barriers on engagement. The dashed lines represent the test for the overall effect of whether the decision aid improves engagement through that pathway.

*Effect of decision aid on barriers; +Effect of barriers on patient engagement.

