4.4 Institutional Randomization

Prior to study activation, each of the 10 participating surgery clinics will be randomly assigned to a time when the clinic crosses over from usual care to intervention. To avoid anticipatory effects, clinics will be blinded to crossover time until the point of implementation. See [Section 4.7](#) for a description of the stratification factors for this study.

Wave	1	2	3	4	5	6	7
Clinics 9-10							
Clinics 7-8							
Clinics 5-6							
Clinics 3-4							
Clinics 1-2							
Usual care group		Implementation period (no data collection)		Intervention group			

Figure 4. Stepped-wedge study design. The effect of the decision aid on patient engagement will be evaluated as a pre/post comparison through the stepped wedge design (years 1-2). Persistent barriers to engagement will be characterized through one-on-one patient interviews (years 2-4). Stakeholder focus groups will inform the identification of targets for adjunct interventions (years 4-5).

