12.1.2 Sample Size and Power Calculations

Co-Primary Objective #1: Based on current patient enrollment, we estimate a sample size of 563 patients. This has been reduced from our original estimate of 1,050 patients. We assume 23 surgeons will participate. Aim 1 has two primary endpoints: PEPI-5 self-efficacy and Active Patient Participation Behaviors (count). We desire a family-wise two-sided Type I error rate of $\alpha=0.05$; under a Bonferroni correction, tests will be conducted with nominal of $\alpha=0.05/2 = 0.025$.

Using the revised analysis model and updated accrual projections, we estimated Fisher's information for the regression parameters when the study will have complete data; inverting that information we obtained an estimate of the standard error for the intervention effect parameter, thereby computing minimally detectable Cohen's-*D* effect size for each primary endpoint at 80% and at 90% power. As a sensitivity analysis, we considered varying estimates of ICCs to ensure robust findings.

Self-Efficacy: Assuming PEPI-5 has a standard deviation (SD) of 4.3 and both within-surgeon and within-site-between surgeon ICC of 0.07, we will have 80% power to detect effects as small as $0.55*4.3=2.4$ and 90% power to detect effects as small as $0.63*4.3=2.7$ on a scale of 5-25. We consider a difference of 2 points to be clinically meaningful.

Active Patient Participation Behaviors: Assuming the active patient participation behavior count has a standard deviation of 23.1 and a within-surgeon ICC of 0.01 and within-site-between surgeon ICC of 0.0001, we have 80% power to detect a difference of $0.50*23.1=11.6$ and 90% power to detect a difference as small as $0.57*23.1=13.2$ on a 0-150 scale. We consider a difference of 10 to be clinically meaningful.

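### Cheap improvement: protect the clinic and surgeon intercepts of the primary model, because testing them out can erase variance shares the plan calls critical and can make the two tests slightly more liberal

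*Combined protocol and SAP*

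**What the plan says.** Section 12.1.1 describes the data as "patients nested within surgeons within surgical clinics, this last level being the formal level of intervention". The primary linear mixed model carries "a surgeon random effect, and a clinic random effect", plus a residual. Section 4.4 fixes the unit of randomisation: "each of the 10 participating surgery clinics will be randomly assigned to a time when the clinic crosses over from usual care to intervention".

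After writing out the equation, section 12.1.1 adds that "we will fully test the variance-covariance structure of the model, while blinded to any treatment effects, which may lead to a more parsimonious model". It gives no test, cut-off, order of testing or term that must stay. It names the SAS procedures but no degrees-of-freedom method for the linear models.

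The same section plans to report the percentage of variance at surgeon and clinic level and comments: "This is critical as it will suggest at what level adjunct interventions may be most effective". Its part on persistent barriers says that those models carry surgeon and clinic random effects, as in Aim 1.

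Section 12.1.2 sets the error target, "We desire a family-wise two-sided Type I error rate of" 0.05, with 0.025 for each of the two endpoints. For PEPPI-5 it assumes "both within-surgeon and within-site-between surgeon ICC of 0.07". For Active Patient Participation Behaviors it assumes 0.01 within surgeon and 0.0001 between surgeons within site.

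**The concern.** The planned model has only two random effects, so a more parsimonious random part means dropping one or both. Two things are then at stake.

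First, a dropped term has no variance share. The plan wants those shares in order to choose the level at which later interventions should act, so a zero produced by a test with little power could point to the wrong level.

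Second, removing a real clustering term makes the standard error of the intervention effect too small. Blinding to the treatment effect stops the model being chosen for its result, but it does not by itself guarantee the size of the test.

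**Working it through.** **Plan's own figures.** 0.05/2 = 0.025, so the two-sided critical value is 2.241. The detectable effect is SE × (2.241 + z for power), which gives multipliers of 3.083 (80%) and 3.523 (90%). From the stated 80% effects, 0.55 × 3.523/3.083 = 0.628 and 0.50 × 3.523/3.083 = 0.571, against 0.63 and 0.57 in section 12.1.2. These agree. The absolute values cannot be checked exactly because the accrual projections are not given. Equal accrual gives a mean SE of 0.168 SD for PEPPI-5, and 0.168 × 3.083 = 0.52 against the stated 0.55, which is plausible.

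**ICCs as variance shares.** The clinic share is the between-surgeon ICC. The surgeon share is the within-surgeon ICC minus the between-surgeon ICC.
- PEPPI-5: clinic 0.07, surgeon 0.07 − 0.07 = 0.
- Active Participation: clinic 0.0001, surgeon 0.01 − 0.0001 = 0.0099.
- Alternative reading for PEPPI-5: 0.07 for each component.

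**Simulation.** From the plan: 563 patients, 23 surgeons, 10 clinics, 7 waves, two clinics crossing per wave from wave 2, no data in the implementation wave, and the fixed effects in the section 12.1.1 equation (without further patient covariates). Assumed, because the documents do not say: post-COVID restart in waves 2–4 by clinic, equal accrual, and backward testing by REML likelihood ratio with cut-offs 2.0, 2.706 and 3.841. Tested-down ranges run over these cut-offs. The main run used 160,000 null trials per setting (Monte Carlo error 0.04–0.05 points). Separate runs of 10,000 to 60,000 trials (error 0.07–0.16 points) repeated it and also did the selection without the intervention term.

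**Variance shares set to zero.** The tested-down figures are nearly the same with and without the intervention term.

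| True share | Both kept | Tested down |
|---|---|---|
| PEPPI-5 clinic, 0.07 (surgeon 0) | 2% | 10–16% |
| PEPPI-5 clinic, 0.07 (surgeon 0.07) | 10% | 48–66% |
| Active Participation surgeon, 0.0099 | 42–44% | 82–91% |

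**Type I error at nominal 2.5%, z test.**

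| Setting (clinic/surgeon) | Both kept | Tested down, term included | Rise if term left out |
|---|---|---|---|
| PEPPI-5 (0.07/0) | 3.1% | 3.3–3.7% | about 0–0.1 points |
| Active Participation (0.0001/0.0099) | 2.6% | 2.9–3.2% | 0.02–0.4 points |
| PEPPI-5 (0.07/0.07) | 2.8% | 3.0–3.1% | about 0–0.16 points |

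With the term included, the PEPPI-5 (0.07/0) rise is 0.24–0.58 points. Of this, 0.21–0.57 comes from the 6–11% of trials that lose both intercepts, and only 0.04 from losing the clinic term alone.

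**Sum over the two endpoints, PEPPI-5 at 0.07/0 (upper bound on family-wise error).**
- Both kept, z: 3.1 + 2.6 = 5.7%.
- Tested down with the term, z: 6.3–6.7% (added before rounding), so the clause adds 0.6–1.0 points.
- Tested down without the term: the clause adds at most about 0.1 + 0.4 = 0.5 points.
- Both kept, Kenward-Roger: 2.5 + 2.1 = 4.6% (a separate run gave 2.62 + 2.09 = 4.71%).

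The 0.7 points between 5.0 and 5.7% are present with no testing at all. Replacing z by t with 535 residual degrees of freedom changes the size by at most 0.05 points, so this part belongs to the missing small-sample method.

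**The case against.** The strongest reply is that the structure is to be tested while blinded to treatment effects, and a natural way to do that is to fit the covariance model without the intervention term. On that reading the added error is close to simulation error for PEPPI-5 and a few tenths of a point at most for Active Participation. This stands, and it limits the error claim to what can happen.

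Second, most of the excess under that reading exists with both intercepts kept, so the testing clause is not its cause. This also stands. Where both PEPPI-5 components are 0.07, one 10,000-trial run even gave a sum below 5% with both kept and z (2.45 + 2.43 = 4.88%, Monte Carlo error about 0.2 points), while the main run gave 5.4%.

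Third, the persistent-barriers text shows an intent to carry both random effects, and nothing says that the variance shares must come from the reduced model. That is fair as to intent. However, it does not limit the testing sentence, and nothing says that the shares come from the full model either.

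Fourth, the Active Participation surgeon share is about 1%, and the kept model reports zero in over 40% of trials anyway. This is correct. The PEPPI-5 clinic share carries the point.

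A reader might also infer that losing the clustering terms makes the tests grossly invalid. Ignoring clustering in every trial would give about 14.6% for PEPPI-5 (20.3% if both components are 0.07). The planned ICCs do not support that inference, because testing drops both PEPPI-5 intercepts in only about 6–11% of trials (under 1% if both components are 0.07).

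**Conclusion.** The point holds as a cheap improvement. The plan permits its only two clustering terms to be tested out, protects neither, and in the same section relies on their variance shares. The loss of shares is the firmer half, because it appears on either reading of the blinding: 10–16% against 2% for the PEPPI-5 clinic share, or 48–66% against 10% if both components are 0.07.

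The effect on error is mild and conditional. It is 0.6–1.0 points on the two-test sum if selection includes the intervention term, and at most about 0.5 points if it does not. One might read the 6.3–6.7% sum as the trial's family-wise error under the plan. The documents do not support that: the figure is an upper bound, it rests on an assumed selection rule, and 5.7% of it arises without any testing. Nor does the clause allow the model to be picked by its result, since it requires blinding.

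The sizes depend on the assumed restart waves, equal accrual and cut-offs. Spreading clinic sizes over 120–300 changed the error rates little: PEPPI-5 3.1% kept and 3.4–3.8% tested down with the term, Active Participation 2.6% and 2.9–3.1%.

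**What to change.** Two separate steps, before any unblinded analysis.

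1. Replace the testing sentence with wording such as: *Clinic and surgeon-within-clinic random intercepts are retained in the primary model whatever their test result. A REML estimate of zero is reported as zero, and variance percentages are taken from this model. The same intercepts are retained if a log-linear model is used for a count endpoint.* This matches the persistent-barriers text.

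2. Add: *In the linear mixed models the intervention effect is tested with Kenward-Roger degrees of freedom.* This does not extend to the fallback, where "log-linear random effect models will be used to estimate the relationship of these endpoints to intervention group".

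The cost is a few sentences, with no new data or model. Step 2 widens intervals by about 3% (PEPPI-5) and 4% (Active Participation) and leaves the Active Participation test slightly conservative at 2.1%. Against both kept with z, simulated power falls from 88.5% to 87.2% for PEPPI-5 (2 points, SD 3.4) and from 87.5% to 85.5% for Active Participation (10, SD 19.1). Against the more liberal tested-down model, Active Participation falls from 88.5–89.0% to 85.5%, a loss of 3.0–3.5 points. These power levels assume equal accrual, so the differences matter more than the levels.
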